8.3. Adverse Events and Serious Adverse Events

The definitions of an AE or SAE can be found in Sections 10.3.1 and 10.3.2, respectively.

An AE will be reported by the participant (or, when appropriate, by a caregiver, surrogate, or the participant's legally authorized representative).

The Investigator and any qualified designees are responsible for detecting, documenting, and recording events that meet the definition of an AE or SAE and remain responsible for following up AEs that are serious, considered related to the study treatment or study procedures, or that caused the participant to discontinue the study treatment (Section 7).

8.3.1. Adverse Events of Special Interest

Table 10 Adverse Events of Special Interest (AESI)

Gastrointestinal (reported as AESI if Grade ≥ 3)			
Diarrhea	Nausea Vomiting		
Eye Disorders (reported as AESI if Grade ≥ 2)			
Retinal Vein Occlusion (RVO)	Uveitis Optic neuropathy		
Retinopathy	Retinal detachment		
Cardiac Disorders (reported as AESI if Grade ≥ 2)			
Ejection fraction decreased	Cardiac failure Left ventricular dysfunction		
Neurologic Disorders (reported as AESI if Grade ≥ 2)			
Confusion	Hallucinations Delirium		
Skin Disorders (reported as AESI if Grade ≥ 3)			
Rash	Acneiform rash		

These are selected, non-serious AEs and SAEs that **must be reported within 24 hours** regardless of relationship to study treatment. For participants who experience signs or symptoms that may be consistent with an AESI, sites are strongly encouraged to immediately notify the Medical Monitor of the event via email and/or phone. Documentation of potential AESIs should occur after discussion between the investigator and the Medical Monitor. Many of these events may also qualify as SAEs. Any event that meets the criteria described in Table 10 must be reported regardless of investigator-determined relationship to study treatment (unless otherwise

specified). Investigators/study coordinators/designated site personnel are required to record these experiences in the eCRF (as described in the eCRF completion guidance document) and to provide supplemental information (such as medical history, concomitant medications, investigations, etc.) about the event. Please note this table lists known AESI, and additional events may be identified during the course of the study.

8.3.2. Time Period and Frequency for Collecting AE and SAE Information

All SAEs and AEs will be collected from the time of signing informed consent/assent until 30 days after the last dose of study treatment at the time points specified in the SoA (Section 1.3, Section 1.4).

Medical occurrences that begin before the start of study treatment but after obtaining informed consent/assent will be recorded as AEs.

All SAEs will be recorded and reported to the Sponsor's safety group (Safety) immediately and under no circumstance should this exceed 24 hours, as indicated in Section 10.3.3 and Section 10.3.4. The Investigator will submit any updated SAE data to Safety within 24 hours of it being available.

To report the SAE, a paper SAE form must be completed, scanned, and emailed Safety at [contact]. The paper SAE form can be found in the Site reference manual. Refer to Section 10.3.4 for more details on reporting SAEs to Safety.

Investigators are not obligated to actively seek AEs and/or SAEs after conclusion of the study participation. However, if the Investigator learns of any SAE, including a death, at any time after a participant has been discharged from the study and considers the event to be reasonably related to the study treatment or study participation, the Investigator must promptly notify the Sponsor.

8.3.3. Method of Detecting AEs and SAEs

The method of recording, evaluating, and assessing causality of AEs and SAEs and the procedures for completing and transmitting SAE reports are provided in Section 10.3.3.

Care will be taken not to introduce bias when detecting AEs and/or SAEs. Open-ended and non-leading verbal questioning of the participant is the preferred method to inquire about AE occurrences.

8.3.4. Follow-up of AEs and SAEs

After the initial AE/SAE report, the Investigator is required to proactively follow each participant at subsequent visits/contacts. All SAEs will be followed until resolution, stabilization, the event is otherwise explained, or the participant is lost to follow-up (as defined in Section 7.3). Within 24 hours of receipt of follow-up information, the Investigator must complete a paper follow-up SAE form and submit any supporting documentation if requested to Safety. Further information on follow-up procedures is given in Section 10.3.3.

8.3.5. Regulatory Reporting Requirements for SAEs

Prompt notification by the Investigator to the Sponsor of an SAE is essential so that legal obligations and ethical responsibilities towards the safety of participants and the safety of a study treatment under clinical investigation are met.

The Sponsor has a legal responsibility to notify both the local regulatory authority and other regulatory agencies about the safety of a study treatment under clinical investigation. The Sponsor will comply with country-specific regulatory requirements relating to safety reporting to the regulatory authority, Institutional Review Boards (IRB)/Independent Ethics Committees (IEC), and investigators.

Investigator safety reports must be prepared for Suspected Unexpected Serious Adverse Reactions according to local regulatory requirements and Sponsor policy and forwarded to Investigators as necessary.

An Investigator who receives an Investigator safety report describing an SAE or other specific safety information (e.g., summary or listing of SAEs) from the Sponsor will review and then file it along with the Investigator's Brochure and will notify the IRB/IEC, if appropriate according to local requirements.

8.3.6. Pregnancy

Details of all pregnancies in female participants and female partners of male participants will be collected after the start of study treatment and until 30 days after the last dose of study treatment.

If a pregnancy is reported, the Investigator should inform the Sponsor within 24 hours of learning of the pregnancy by completing a paper pregnancy form and submitting to Safety (refer to Section 10.4 for reporting details).

Abnormal pregnancy outcomes (e.g., spontaneous abortion, fetal death, stillbirth, congenital anomalies, ectopic pregnancy) are considered SAEs.

8.4. Treatment of Overdose

For this study, any administration of study treatment greater than 150% of the BSA assigned maximum total daily dose within a 24-hour period will be considered an overdose. Noncompliance with the intermittent dosing schedule does not in itself constitute a study treatment overdose.

In the event of an overdose, the Investigator should:

- 1. Contact the Medical Monitor immediately (refer to Section 10.10.3 for contact information).
- 2. Closely monitor the participant for any AE/SAE and laboratory abnormalities for at least 4 days.

3. Document the quantity of the excess dose as well as the duration of the overdose in the eCRF.

Decisions regarding dose interruptions or modifications will be made by the Investigator in consultation with the Medical Monitor based on the clinical evaluation of the participant.

8.5. Pharmacokinetics

Sparse PK samples will be collected during the Treatment Phase of the study to inform development of a population PK model of mirdametinib (PD-0325901) and its active metabolite (PD-0315209). See Section 10.8 for the study sampling schedule.

- Whole blood samples of approximately 3 mL will be collected for measurement of plasma concentrations of PD-0325901 and PD-0315209. Refer to the SoA (Section 1.3) and Section 10.8 for details on PK sampling time points. Each plasma sample will be divided into 2 aliquots (1 each for PK and a back-up). Samples may be stored for a maximum of 10 years (or according to local regulations) following the last participant's last study visit at a facility selected by the Sponsor to enable further analysis of kinetic responses to PD-0325901.
- All efforts will be made to obtain the pharmacokinetic samples at the exact nominal time relative to dosing. However, samples obtained within 10 minutes of the nominal time (± 10 minutes) from dosing will not be captured as a protocol deviation if the exact time of the sample collection is noted on the source document and eCRF. The actual date and time (24-hour clock time) of each sample will be recorded.
- Instructions for the collection, handling, and shipment of pharmacokinetic samples will be in the central laboratory manual.
- Genetic analyses will not be performed on these samples. Participant confidentiality will be maintained.
- Any changes in the timing or addition of time points for any planned study assessments
 must be documented and approved by the Sponsor or Medical Monitor and then
 archived in the Sponsor and Site study files but will not constitute a protocol
 amendment.

8.6. Pharmacodynamics

As a marker of effects of PD-0325901, biomarkers indicative of inhibition of downstream targets of MEK (e.g., ERK phosphorylation) will be measured in PNs as described in Section 8.8.

Percutaneous core needle biopsies from participants \geq 18 years of age will be collected as described in the Treatment Phase SoA (Section 1.3) and Section 10.8. These samples are required for pharmacodynamic biomarker analysis, but they will not be processed for DNA (tumor mutagenesis evaluation).

Instructions on the collection, processing, storage and shipment will be provided in the laboratory manual.

Samples may be stored for a maximum of 10 years (or according to local regulations) following the last participant's last study visit at a facility selected by the Sponsor to enable further analysis of PD responses to PD-0325901.

8.7. Genetics

Genetics will not be assessed in this study.

8.8. Biomarkers

As discussed in Section 8.6, PD biomarkers will be evaluated in this study.

Two (2) percutaneous core needle biopsies from participants \geq 18 years of age will be collected as described in the Treatment Phase SoA (Section 1.3) and Section 10.8. These samples are required for pharmacodynamic biomarker analysis, but they will not be processed for DNA (tumor mutagenesis evaluation)

- Samples will be tested for biomarkers indicative of inhibition of downstream targets of MEK (e.g., ERK phosphorylation) to evaluate their association with the observed clinical responses (e.g., tumor volume reduction) to PD-0325901 and its metabolite(s).
- Details on processes for collection, processing, shipment, and destruction of these samples can be found in laboratory manual.

Samples may be stored for a maximum of 10 years (or according to local regulations) following the last participant's last study visit at a facility selected by the Sponsor to enable further analysis of biomarker responses to PD-0325901.

8.9. Medical Resource Utilization and Health Economics

Health Economics/Medical Resource Utilization and Health Economics parameters are not evaluated in this study.

9. Statistical Considerations

9.1. Statistical Hypotheses

The null hypothesis for the participants \geq 18 years of age at Baseline (the adult population) is that the objective response rate (ORR) is less than or equal to 23%. The alternative hypothesis is that the ORR is greater than 23%. The null hypothesis for participants 2 to 17 years of age at Baseline (the pediatric population) is that the ORR is less than or equal to 42%. The alternative hypothesis is that the ORR is greater than 42%.

9.2. Sample Size Determination

MEK-NF-201 is a single-stage, single-arm, open-label, potentially registrational study to evaluate the efficacy, safety, and tolerability of mirdametinib (PD-0325901) in participants ≥ 2 years of age with an inoperable NF1-associated PN that is causing significant morbidity.

Approximately 150 participants will be screened in this study to assure approximately 100 participants are assigned to the open-label treatment with mirdametinib. These 100 participants will be stratified by age, with 50 participants ages 2 to 17 years for the pediatric cohort and 50 participants \geq 18 years of age for the adult cohort.

Sample size assumptions for the pediatric population are based on the interim ORR of 66% from the SPRINT study conducted by Gross et al. The SPRINT study enrolled 50 patients aged 3-18 years with inoperable morbid PNs (Gross, 2018). For the pediatric cohort, an ORR of at least 66%, as mentioned above, will result in a lower bound of 55% for a one-sided 95% CI. Under these assumptions, the Type II error of a one-sided Z-test is under 20% for any null hypothesis of ORR \leq 49%.

Sample size assumptions for the adult population are based on an ORR of at least 42%, as determined from a previous SpringWorks interim analysis of phase 2 mirdametinib study in adult participants. With 50 participants in this cohort, the response rate of 42% will result in a lower bound of the one-sided 95% CI that excludes 30%. Under these assumptions, the Type II error of a one-sided Z-test (using normal approximation to the binomial distribution) at a 95% statistical significance level is below 20% for any null hypothesis of $ORR \le 24\%$.

For the safety analysis, there is a 95% chance of observing at least one adverse event that occurs at an underlying rate of 3.0 % in a sample size of 100 participants.

The primary and secondary endpoints in the pediatric and adult cohorts will be analyzed separately since each cohort is age-dependent, as shown by the difference in tumor growth rates between pediatric patients and adult patients (Dombi 2007, Nguyen 2012, Tucker 2008). Other secondary endpoints may be pooled, if appropriate to the endpoint.

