9.4.1. Efficacy Analyses

Endpoint	Statistical Analysis Methods
Primary	The primary endpoint is objective response rate (ORR) at the end of the Treatment Phase, defined as the proportion of participants who have a \geq 20% reduction in target tumor volume as compared to Baseline. Exact 1-sided binomial 95% confidence intervals will be calculated on the response rate. Participants who are missing all response data will be treated as non-responders. Participants who discontinue early from the study without responding will be treated as non-responders. Objective response rate will be calculated separately by age cohort.
Secondary	Duration of response (DOR) in participants who meet the criteria for ORR will be calculated as the time between the first instance of response until the date of progression or censored date (censorship rules will be specified in the analysis plan). The DOR will be analyzed using Kaplan Meier method; median duration of response and the 95% CIs on the intervals will be calculated. Kaplan Meier will be used for the overall population, and also on cohort groups. Details of censoring methods and sensitivity analyses will be described in the statistical analysis plan.
	Time-to-Response will also be calculated as the time between first dose and the first date of objective response. Univariate statistics will be reported.
	Change from baseline in overall clinical status: All participants and/or parents/legal representatives will complete a HRQOL (PedsQL) to assess overall change in clinical status.
	Change from baseline in pain: Pain will be measured using an 11-point numeric rating scale (NRS-11) and the Pain Interference Index. For the NRS-11, participants will report overall pain in the location of the primary target tumor. The Pain Interference Index questionnaire will assess self-reported and parent/legal representative reported consequences of pain on relevant aspects of one's life over the previous 7-day period.
Exploratory	Progression Free Survival is defined as the time in months from the first dose to the date of a \geq 20% increase in tumor volume or death. Participants who do not meet the criteria for progression will be censored (censorship rules will be specified in the analysis plan). The PFS will be analyzed using Kaplan Meier methods; median PFS and the 95% CIs on the intervals will be calculated. Details of censoring methods and sensitivity analyses will be described in the statistical analysis plan.

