6.11.1 Primary Efficacy Analysis

To assess the primary efficacy endpoint, confirmed ORR by the end of the Treatment Phase as assessed by BICR will be presented as a percentage alongside the corresponding 2-sided 95% Clopper-Pearson Cl and the p-value from a one-sample two-sided binomial test for the confirmed ORR compared to the minimum clinically relevant response rates defined in Section 5.2. The overall assessment of the endpoint will be based on the exclusion of the minimum clinically relevant response rate by the lower tail of the 95% Cl.

Document: S:\Q_146\Q_03974\MEK-NF-201\Prog_Stat\Documentation\SAP\MEK-NF-201 SAP v1.0.0.docx

Author:

All tumor data from MRI assessments will be listed across both the Treatment and LTFU Phases.

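### Protocol 9.2 plans the pediatric cohort with a normal approximation, but the endpoint is analysed with an exact interval, which gives slightly less favorable figures

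*Protocol*

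**What the plan says.** Protocol 9.2 plans the pediatric cohort "with 50 participants ages 2 to 17 years for the pediatric cohort" and takes its rate from an external selumetinib trial: "Sample size assumptions for the pediatric population are based on the interim ORR of 66% from the SPRINT study". At that rate, it says, the cohort "will result in a lower bound of 55% for a one-sided 95% CI". It adds that "the Type II error of a one-sided Z-test is under 20% for any null hypothesis of ORR" up to 49%. The pediatric paragraph names no method for the bound and no alpha for the test. The adult paragraph is more explicit about its own Z-test: "using normal approximation to the binomial distribution) at a 95% statistical significance level is below 20"%.

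The analysis sections use a different method. Protocol 9.4.1: "Exact 1-sided binomial 95% confidence intervals will be calculated on the response rate". SAP 6.11.1 has the confirmed response rate "presented as a percentage alongside the corresponding 2-sided 95% Clopper-Pearson" interval and judges the endpoint on whether the lower limit excludes the minimum relevant rate.

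The pediatric null is 42% in Protocol 9.1. SAP 5.2 recalls that value and updates it to 20%. SAP 2.3 gives a separate pediatric planning statement: 32/50 (64%) puts the lower 95% limit above 49%. It states no pediatric power.

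**The concern.** A reader who applies the interval in Protocol 9.4.1 to 33 responders out of 50 will not obtain 55%, and a reader who computes the exact test of a 49% null will not obtain a Type II error under 20%. This sentence is the only pediatric Type II statement in either document, and Protocol 9.2 calls the study potentially registrational, so its operating characteristics should be those of the rule that will be applied. What is at stake is whether the stated planning figures can be relied on. A larger question would be whether 50 children are enough; that is checked below.

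**Working it through.** **Inputs.** n = 50 and rate 66%, i.e. 33/50 (Protocol 9.2). Planning null 49% (Protocol 9.2). Tested nulls 42% (Protocol 9.1) and 20% (SAP 5.2, updated). One-sided alpha is 0.05 for the protocol rule and 0.025 in the lower tail for the SAP rule. The pediatric Z-test alpha is not stated; 0.05 is assumed from the one-sided 95% interval and the adult paragraph. It is also the value that reproduces the text: at 0.025, with the variance at the alternative, power at a 49% null is only 71.8%.

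**Step 1: reproduce the protocol's figures.** The standard error at 66% is √(0.66 × 0.34 / 50) = 0.0670.

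- Wald lower bound: 0.66 − 1.645 × 0.0670 = 0.5498, which rounds to 55%.
- Z-test of 49%, variance at the alternative: power = Φ(0.17 / 0.0670 − 1.645) = Φ(0.893) = 81.4%, so Type II error is 18.6%. The highest null with 80% power is 0.66 − (1.645 + 0.842) × 0.0670 = 49.3%, which matches the stated limit of 49%.
- The same formula gives a limit of 24.6% for the adult cohort at 42%, matching the stated 24%. This was evidently the method used.

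With the variance taken at the null instead, √(0.49 × 0.51 / 50) = 0.0707, power is Φ((0.17 − 1.645 × 0.0707) / 0.0670) = Φ(0.802) = 78.9%, so Type II error is 21.1%. The stated figure therefore depends on the variance convention.

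**Step 2: exact lower bound for 33/50.** The Clopper-Pearson lower limit is the alpha quantile of Beta(33, 18).

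- One-sided 95%: 53.5%.
- Two-sided 95%: 51.2%.

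**Step 3: exact Type II error at a true rate of 66%.** For each null, take the smallest count whose upper binomial tail is at most alpha, then the probability of falling short of it at 66%.

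| Null | Rule | Responders needed | Type II error | Power |
|---|---|---|---|---|
| 49% | one-sided 0.05 | 31/50 | 22.6% | 77.4% |
| 49% | lower tail 0.025 | 32/50 | 32.3% | 67.7% |
| 47% | one-sided 0.05 | 30/50 | 14.8% | 85.2% |
| 45% | lower tail 0.025 | 30/50 | 14.8% | 85.2% |
| 42% | one-sided 0.05 | 28/50 | 5.2% | 94.8% |
| 42% | lower tail 0.025 | 29/50 | 9.1% | 90.9% |
| 20% | lower tail 0.025 | 17/50 | below 0.1% | above 99.9% |

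The 47% and 45% limits follow from the exact lower limits for 30/50, which are 47.4% (one-sided) and 45.2% (two-sided). Any higher whole-percent null needs at least 31/50, and Type II error is then at least 22.6%.

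**Step 4: the SAP's own figure.** The two-sided Clopper-Pearson lower limit for 32/50 is 49.2%, so SAP 2.3 is correct on the exact method.

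**Step 5: the adult paragraph on the same yardstick.** 21/50 has an exact one-sided lower limit of 30.1%, which does exclude 30%. At a 24% null and a true rate of 42%, the one-sided exact rule needs 18/50 and has Type II error 15.8%. The SAP's two-sided rule needs 19/50 and has Type II error 23.8%.

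**The case against.** The strongest reply is that the Protocol 9.2 sentence claims something about a Z-test, and for one standard form of that test the claim is true. That stands. The sentence contains no arithmetic slip, and the fault is that planning and analysis use different methods. It does not rescue the 55% bound, which is stated with no method, while the only one-sided 95% interval the protocol plans for this endpoint is exact.

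Second, no planned analysis tests 49%. A reader might infer from a Type II error of 22.6% or 32.3% that the pediatric cohort is underpowered. The documents do not support that: at the assumed 66%, exact power exceeds 90% against either tested null.

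Third, SAP 2.3 has already moved the pediatric bound to an exact two-sided basis and is correct. It gives no pediatric power, however, so the Type II statement in Protocol 9.2 is not replaced anywhere.

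Fourth, a reader might infer that the error is peculiar to the pediatric paragraph. That holds only under the one-sided exact rule; under the SAP's two-sided rule the adult limit of 24% is missed as well.

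Finally, the assumed rate matters more than the choice of interval. SAP 7.1 reports that the external trial's rate by independent central review was 44%. At a true 44%, exact power against 42% would be 5.9% (one-sided) or 3.2% (two-sided), and against 20% it would be 94.3% (two-sided). This is a separate matter from the point made here.

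**Conclusion.** The concern holds as a minor inconsistency of method. The protocol's pediatric lower bound overstates the exact result by about 1.5 percentage points one-sided (55% against 53.5%), or 3.8 against the SAP's interval (51.2%). The stated limit for nulls with Type II error under 20% is 2 points too high one-sided (49% against 47%), or 4 points two-sided (45%). The sample size, the decision rule and the power against the tested nulls are unaffected at the assumed 66%. The result rests on n = 50 with no loss, a true rate of 66%, and a one-sided alpha of 0.05 for the unstated pediatric Z-test.

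**What to change.** - **Protocol 9.2, pediatric paragraph:** state that 33/50 gives an exact one-sided 95% lower bound of 53.5%, and that Type II error at 66% is below 20% for nulls up to 47%. Name the exact binomial method.
- **SAP 2.3:** keep the 32/50 statement. Beside it add the two-sided figures: a lower bound of 51.2% for 33/50, and Type II error below 20% for nulls up to 45%.
- **Power at the tested nulls:** in the same place, give exact power at 66%: 94.8% one-sided or 90.9% two-sided against 42%, and above 99.9% against 20%. This shows that the restated limits do not call the cohort size into question.
- **Adult paragraph:** note that the 24% limit holds under the one-sided exact rule (Type II error 15.8%) but not under the two-sided rule (23.8%).

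The cost is a text change. No design element, sample size or analysis changes; the restated bound and null limits are slightly less favorable.
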